4.2. Scientific Rationale for Study Design

As is typical in the case for FIH studies, the population planned for this study will be healthy adult male and female participants of nonchildbearing potential. Female participants will be confirmed not to be of childbearing potential because reproductive toxicity studies with PF-06954522 have not been conducted. In male participants, appropriate measures are expected to be followed to minimize potential transfer of PF-06954522 via semen to partners (see Appendix 4).

The highest anticipated C_{max} and AUC_{24} of PF-06954522 will not exceed the pre-defined human exposure stopping limits. Furthermore, to permit an unbiased assessment of safety, the participants' treatment assignments (active treatment versus placebo) will be blinded to both site staff (except those involved in preparation of doses) as well as the study participants. However, to permit real-time review of the safety, tolerability, and PK data, a limited number of sponsor study team members will be unblinded.

Given the current study is the first time PF-06954522 will be administered to humans, an escalating single, oral dose crossover design is planned with careful assessment and ongoing review of safety, tolerability, and PK data of PF-06954522. The crossover design will permit both a within- and between-participant assessment of safety/tolerability and PK at multiple dose levels and placebo. The optional Cohort 2 may be included if, based on emerging data from the Cohort 1, it is deemed necessary to meet the objectives of this study.

The optional Cohort 3 (Japanese participants) is included in this study to potentially collect safety, tolerability and PK data that may facilitate development of PF-06954522 in Japan. Continuous cardiac monitoring via telemetry will not be performed in this cohort, and the schedule of ECG/vital sign measurements may be less intensive (see SoA), because the doses administered in this cohort would have been investigated and deemed sufficiently safe in a previous cohort.

For a given participant, it is planned that dosing will be separated by at least 7 days. This planned washout interval is deemed sufficient CCI

(see Section 4.3.1). In addition, PK samples are planned to be collected over 72 hours post-dose to ensure sufficient characterization of PK profile and to account for any

uncertainty in PK prediction. However, sampling times, duration of sampling, and/or the length of the interval between doses may be modified and/or extended based on emerging PK. The planned doses in the dose escalation sequence (Table 3) may be modified or repeated, as guided by emerging safety, tolerability, and PK data but will follow the dose-escalation rules defined in Section 6.6.1.

Dosing will initially be conducted in the fasted state (at least 10 hours) to facilitate management of any AEs which may occur shortly after dosing.

However, as it is expected that in future studies PF-06954522 may be administered in the fed state, the effect of food (high-fat breakfast) will be assessed in this study to explore not only the PK but also the safety and tolerability profile of PF-06954522 in the condition which it will be most likely administered in the next stages of development.

CCI

Changes in temperature and blood pressure were also noted in nonclinical toxicity studies, and these parameters will be measured through serial assessments of vital signs. In addition, calcitonin, amylase, lipase, and total bile acids will be assessed in the study due to elevations (total bile acids) observed in nonclinical toxicity studies (see Section 2.2.4), and these laboratory parameters have been shown to increase in patients treated with marketed GLP-1R agonists.[13] Similarly, based on the potential risk of thyroid C-cell tumor associated with marketed GLP-1R agonists, participants with a personal or family history of MTC or MEN2, or participants with suspected MTC will be excluded. To ensure that participants with undiagnosed diabetes or thyroid dysfunction are not enrolled, HbA1c, and TSH levels will also be assessed at screening.

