4.3.3. Human Exposure Stopping Limits

the NOAEL doses in the 8-week GLP toxicity studies were which were the highest doses tested in those respective studies. At the NOAEL in monkeys (the most sensitive toxicology species), the total C_{max} and AUC₂₄ were mg/mL and mg/mL, respectively. Therefore, the human exposure stopping limits for PF-06954522 are based on the unbound exposures (CCI) observed at the NOAEL in monkeys in the 8-week GLP toxicity study. After correcting for species dependent plasma protein binding in monkeys and humans:

- The human PF-06954522 total C_{max} limit is CCl ng/mL.
- The human PF-06954522 total AUC₂₄ limit is CC ng•h/mL.

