- c. Unbound exposure values calculated after correcting for plasma protein binding in humans (CCI)
- d. Safety margins at the proposed doses were calculated based on the human exposure limits (total

 Which were based on the NOAEL exposures in the 8-week NHP GLP toxicity study after correcting for species difference in plasma protein binding.

Beyond the starting dose, the planned dose escalation procedure will be dictated by the rules summarized in Section 6.6.1. Assessment of the safety, tolerability, and PK after each single dose level will be conducted before escalating to the next dose level. The dose/exposure-escalation increments are planned to be up to approximate semi-logarithmic increases in exposure from the previous highest dose level that has been evaluated. If exposure exceeds the projected therapeutic range, or if changes in safety parameters are observed, smaller dose-escalation steps may be implemented. Dose-escalation is envisioned to proceed up to the highest dose deemed to be well tolerated with an acceptable safety profile, achievement of plasma exposures equivalent to the PK stopping limits (see Section 6.6.1).

The actual dose levels, target exposures, and/or dose level increments may be adjusted (higher or lower) during the study based on emerging human safety, tolerability, and PK data, but projected exposures will not exceed the predefined human exposure limits. Dose levels may also be repeated if warranted.

When the assessment of the effect of food on the PK of PF-06954522 is conducted, the dose level will be selected based on emerging safety, tolerability, and PK data from previous periods of this study. This will be assessed at a dose level that has been previously administered fasted within the same cohort (as outlined in Section 4.2).

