6.6.1. Dose Escalation and Stopping Rules

Dose escalation stopping rules will be used to determine whether the maximal tolerated dose has been attained. Dose escalation may be stopped if it is determined that the limits of safety and/or tolerability have been reached. This decision will be made after a discussion takes place between the sponsor study team and the investigator. The sponsor study team may not overrule the investigator's decision to stop dose escalation. If dose escalation is stopped because of any of these criteria, additional cohorts may receive the same or lower doses of the study intervention.

The dose escalation will be terminated based on the following criteria:

- If 50% or more of the participants receiving active drug at a given dose level (but not
 participants receiving placebo) develop similar clinically significant laboratory, ECG,
 or vital sign abnormalities, in the same organ class, indicating dose-limiting
 intolerance.
- Severe nonserious AEs, considered as, at least, possibly related to study intervention administration, in 2 participants at a given dose level (but not participants receiving placebo), independent of within or not within the same system organ class, indicating dose-limiting intolerance.
- Dosing will be paused for any SAE that occurs in a participant receiving active treatment until causality is fully assessed by the PI and sponsor. Dosing may resume if the SAE is determined to be not drug-related by the PI and sponsor. If the SAE is determined to be either drug-related or unknown, either dosing will cease or the SAE will be evaluated by the sponsor's protocol review committee (or similar review group), which is independent of the study team and investigators. If the protocol review committee determines that dosing may resume, a plan that mitigates risks to participants with the resumption of dosing will be implemented. Such a plan could include a revision of inclusion/exclusion criteria, repeating or reducing the dose, or adding appropriate safety monitoring.
- It is determined that the limit of safety and/or tolerability has been reached. This
 decision will be made following discussions between the study team and the
 investigator.
- Other findings that, at the discretion of the study team and investigator, indicate that dose escalation should be halted.
- If, at any dose level, the average exposure reaches or exceeds the PK stopping limits:

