- If, based on the observed data, the group mean C_{max} or AUC (based on total plasma concentration) of the next planned dose is projected to exceed the escalation limits, that dose will not be explored. Modified doses may be explored if they are not expected to exceed PK stopping criteria.

The highest dose evaluated in this study will not exceed mg.

Progression to the next dose will occur if the last dose was well tolerated and after satisfactory review of the available safety and PK data.

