9.3.2.1. Derivation of PF-06954522 PK Parameters

The plasma PK parameters for PF-06954522, following oral dose administration, will be derived from the plasma concentration-time profiles using standard noncompartmental methods as detailed in Table 4, as data permit. Actual PK sampling times will be used in the derivation of PK parameters. If actual PK sampling times are not available, nominal PK sampling times will be used in the derivation of PK parameters.

Table 4. Plasma PF-06954522 PK Parameters

Parameter	Definition	Method of Determination
AUClast	Area under the plasma concentration-time profile from time 0 to the time of the last quantifiable concentration (C _{last})	Linear/Log trapezoidal method
AUCinf*	Area under the plasma concentration-time profile from time 0 extrapolated to infinite time	AUC _{last} + (C _{last} */k _{el}), where C _{last} * is the predicted plasma concentration at the last quantifiable timepoint estimated from the log-linear regression analysis
Cmax	Maximum plasma concentration	Observed directly from data
Tmax	Time for C _{max}	Observed directly from data as time of first occurrence
t _{1/2} *	Terminal elimination half-life	Loge(2)/kel, where kel is the terminal phase rate constant calculated by a linear regression of the log-linear concentration-time curve. Only those

Parameter	Definition	Method of Determination
		data points judged to describe the terminal log-linear decline will be used in the regression.
CL/F *	Apparent clearance	Dose/AUCinf
V _z /F *	Apparent volume of distribution	Dose/(AUCinf·kel)
AUClast(dn)	Dose-normalized AUClast	AUClast/Dose
AUCinf(dn)*	Dose-normalized AUCinf	AUCinf/Dose
C _{max} (dn)	Dose-normalized C _{max}	C _{max} /Dose

Plasma PF-06954522 PK Parameters Table 4.

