# 3.2. Secondary Endpoint(s)

Blood samples for PK analysis of PF-06954522 will be taken according to the SoA in the protocol.

The plasma PK parameters for PF-06954522, following oral dose administration, will be derived from the plasma concentration-time profiles using standard noncompartmental methods as detailed in Table 2, as data permit. Table 2 shows the analysis scale and method for each parameter.

In all cases, actual PK sampling times will be used in the derivation of PK parameters. If actual PK sampling times are not available, nominal PK sampling times will be used in the derivation of PK parameters.

The following plasma PK parameters as described in Table 2 will be determined:

Table 2. Summary of PF-06954522 plasma PK parameters to be calculated.

Parameter	Definition	Method of Determination	Analysis Scale	Analysis Method
AUC inf *	Area under the plasma concentration-time profile from time 0 extrapolated to infinite time	AUC last + (C last */k el ), where C last * is the predicted plasma concentration at the last quantifiable timepoint estimated from the log-linear regression analysis	ln	A, D
AUC last	Area under the plasma concentration-time profile from time 0 to the time of the last quantifiable concentration (C last )	Linear/Log trapezoidal method	ln	A, D
$C_{max}$	Maximum plasma concentration	Observed directly from data	ln	A, D
$T_{\text{max}}$	Time for Cmax	Observed directly from data as time of first occurrence	R	D
t 1/2 *	Terminal elimination half-life	Log e (2)/k el , where k el is the terminal phase rate constant calculated by a linear regression of the loglinear concentrationtime curve. Only those data points judged to describe the terminal log-linear decline will be used in the regression.	R	D

\*=if data permits.

Abbreviations: A=analyzed using a statistical model (if applicable); D=displayed with descriptive statistics as outlined in Table 5 in Section 6.2; ln=natural-log transformed; R = raw (untransformed).

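### Does the absence of AUC24 from the listed PK parameters leave the exposure ceiling uncheckable?

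*Protocol*

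**What the plan says.** Protocol Section 4.3.3 defines two limits, introduced by "The human PF-06954522 total C_{max} limit is" and "The human PF-06954522 total AUC₂₄ limit is"; the values are blacked out. Section 4.2 ties the design to the same pair: "The highest anticipated C_{max} and AUC_{24} of PF-06954522 will not exceed the pre-defined human exposure stopping limits". Table 3 in Section 4.3.4 gives predicted Cmax and AUC24 for each dose with a margin for each, and its footnote says that "Safety margins at the proposed doses were calculated based on the human exposure limits".

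Section 6.6.1 applies the limits in two bullets. The first acts on observed data, "If, at any dose level, the average exposure reaches or exceeds the PK stopping limits", and what follows its colon is not visible in the public copy. The second bars a dose if "the group mean C_{max} or AUC (based on total plasma concentration) of the next planned dose is projected to exceed the escalation limits". It names no interval for AUC.

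The parameter lists are readable. Protocol Table 4 has AUClast, AUCinf ("Area under the plasma concentration-time profile from time 0 extrapolated to infinite time"), Cmax, Tmax, half-life, CL/F, Vz/F and dose-normalised versions. The SAP says "The following plasma PK parameters as described in Table 2 will be determined" and gives AUCinf, AUClast, Cmax, Tmax and half-life; its Table 3 adds the dose-normalised measures, CL/F and Vz/F. AUC24 is in none of these, nor in SAP Table 5, and SAP Section 2.1 records no departure from the protocol.

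**The concern.** A limit is normally compared with the same quantity measured in the study. Here the AUC limit covers 24 hours, while the listed areas run to the last quantifiable sample (up to 72 h) or to infinity. Someone working only from the parameter tables might set a 72 h or extrapolated area against a 24 h limit, or conclude that the comparison could not be made.

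The ceiling is one of the rules that ends escalation in a first-in-human study, and the Table 3 margins rest on it. A mismatch could distort the apparent margin, and the report would have no tabulated AUC24 beside the limit.

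**Working it through.** There is no plan figure to reproduce, because the limits, the Table 3 values and the projected half-life are all blacked out. The check has three parts.

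**1. Can the ceiling be checked from what is planned?**

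- *Cmax:* derived in protocol Table 4 and summarised in SAP Table 5. It compares directly with the Cmax limit.
- *AUC24:* the Schedule of Activities draws PK samples at 0, 0.5, 1, 2, 3, 4, 6, 8, 10 and 12 h on Day 1, then at 24, 36, 48 and 72 h. Section 6.6 requires PK data to at least 24 h before the next dose level. SAP Section 6.2 lists every concentration with its actual time. The linear/log trapezoidal rule in Table 4, stopped at 24 h, gives AUC24.
- *Accuracy:* in a one-compartment oral model (assumed half-life 3 to 36 h, ka 0.5 to 2 per h), the trapezoidal AUC24 at these times was 0.3% to 1.4% below the true value. No added sample is needed.

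**2. Which AUC does Section 6.6.1 mean?**

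The projection bullet points to limits defined elsewhere. The only AUC limit visible in the protocol is the AUC24 limit in Section 4.3.3. Section 4.2 and Table 3 use the same interval, and the overdose definition in Section 6.8 ties the stopping limit to a 24-hour window. The hidden text after the colon in the first bullet may also name it. No passage tells anyone to use AUClast or AUCinf for this comparison.

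**3. If the wrong area were used, how large would the error be, and in which direction?**

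The model has the structure named under Table 3. The half-life range and ka = 1/h are assumptions. For unit dose over volume, with ke = ln 2 / half-life:

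- AUC(0–T) = ka/(ka − ke) × [(1 − exp(−ke·T))/ke − (1 − exp(−ka·T))/ka]
- AUCinf = 1/ke

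Worked case, half-life 12 h: ke = 0.05776 and ka/(ka − ke) = 1.0613.

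- AUC24 = 1.0613 × (0.75/0.05776 − 1) = 12.72
- AUC72 = 1.0613 × (0.984375/0.05776 − 1) = 17.03, ratio 1.339
- AUCinf = 17.31, ratio 1.361

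| Half-life (h) | AUC72/AUC24 | AUCinf/AUC24 | Apparent margin as a share of the true one (24/72) |
|---|---|---|---|
| 4 | 1.019 | 1.019 | 0.98 |
| 6 | 1.076 | 1.076 | 0.93 |
| 8 | 1.156 | 1.159 | 0.87 |
| 12 | 1.339 | 1.361 | 0.75 |
| 18 | 1.592 | 1.703 | 0.63 |
| 24 | 1.796 | 2.061 | 0.56 |
| 36 | 2.083 | 2.796 | 0.48 |

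The last column is 1 divided by the second. If the last quantifiable sample is at 24 h or later, AUClast is at least as large as AUC24 from the same samples. An AUClast at or below the limit then shows that AUC24 is too. With data cut at 24 h and a quantifiable 24 h sample, the two are the same quantity.

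The exception is a profile that becomes unquantifiable before 24 h. With a 3 h half-life, ka of 1 or 2 per h and a quantification limit at 1% of Cmax, the last usable sample is at 12 h and AUClast is 0.912 or 0.920 of AUC24, so 8% to 9% low. With the quantification limit at 0.1% of Cmax, the 24 h sample is quantifiable and the ratios are 0.989 and 0.986, which is only the trapezoidal error. The assay limit is fixed, so it is a smaller share of Cmax at higher concentrations. The shortfall therefore shrinks as exposure approaches the ceiling.

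**The case for a change.** The strongest case is that a quantity which can stop a first-in-human escalation should be written down rather than left to be inferred. Section 6.6 sets 24 h as a minimum, so one review might hold data to 24 h and another to 72 h. AUClast would then mean different things against a fixed limit. It is only a one-sided check: a value above the limit settles nothing and could end escalation early. Adding one row to the parameter tables would cost almost nothing.

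Much of this stands. AUC24 is missing from tables that can be read in full, so redaction does not explain the omission, and AUClast cannot replace AUC24 unless the half-life is short. But the argument needs a team to set aside the interval attached to its own limit in Section 4.3.3 and substitute another area, and no text leads there. Protocol Table 4 and the SAP tables serve the study's PK endpoints. Escalation is decided on preliminary PK data in unblinded sponsor review (Sections 6.4.3 and 6.6), and Section 9.3.2.2 allows further PK analyses. Observed margins to the limits are not an endpoint in Section 3, so their absence from the planned tables leaves no stated objective unmet.

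**Conclusion.** The omission is real but minor. The AUC limit is on AUC24, and the parameter tables do not list it. The ceiling can still be checked: Cmax is reported, and AUC24 follows from samples already scheduled, to within about 1.4% in the assumed model. Read together, the sections give one sensible meaning for AUC in Section 6.6.1, and no stated rule produces a wrong escalation decision or endpoint result.

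The possible misreading runs from about 2% at a 4 h half-life to 108% at 36 h for the 72 h area, and to about 180% at 36 h for AUCinf. These figures rest on an assumed model and half-life range and on a comparison that the plan does not call for. With profiles quantifiable to 24 h, the error would make exposure look higher and the margin smaller, so it leads away from exceeding the ceiling. Naming AUC24 in the tables would be tidier but would alter no decision or result, so no change to the plan follows.

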4.2.1. Choice of Contraception/Barrier Requirements

Studies to evaluate the developmental toxicity of PF-06954522 have not been conducted. Therefore, female participants will be confirmed to be of non-childbearing potential, the use of a highly effective method of contraception is required for male study participants (see Appendix 4), and is recommended for partners of male participants who are WOCBP.

4.3. Justification for Dose

4.3.1. Human PK Prediction

Human PK of PF-06954522 were predicted using a combination of human in vitro and nonclinical in vivo data.

4.3.2. Predicted Human Efficacious Dose and Concentration

CCI	
	This dose of PF-06954522 has been predicted based
on exposure-response modeling of ^{CCI}	
	and is projected to achieve a
similar pharmacological response CCI	
CCI	

4.3.3. Human Exposure Stopping Limits

the NOAEL doses in the 8-week GLP toxicity studies were which were the highest doses tested in those respective studies. At the NOAEL in monkeys (the most sensitive toxicology species), the total C_{max} and AUC₂₄ were mg/mL and mg/mL, respectively. Therefore, the human exposure stopping limits for PF-06954522 are based on the unbound exposures (CCI) observed at the NOAEL in monkeys in the 8-week GLP toxicity study. After correcting for species dependent plasma protein binding in monkeys and humans:

- The human PF-06954522 total C_{max} limit is CCl ng/mL.
- The human PF-06954522 total AUC₂₄ limit is CC ng•h/mL.

4.3.4. Rationale for Dose Selection

The safety, tolerability, and plasma PK of PF-06954522 after administration of single escalating oral doses across a wide dose/exposure range will be evaluated in this study. The starting dose and subsequent dose escalation steps proposed in this study were determined using the projected human PK of PF-06954522, the available nonclinical safety data, and the anticipated pharmacological effect, and considering that this is a well-precedented mechanism for which multiple GLP-1R agonists are marketed products.

Considering all the above along with the precedent of the pharmacological mechanism (in addition to the marketed peptide GLP-1R agonists, several oral small molecule GLP-1R agonists are in clinical development)[14,15], it is anticipated that the marketed peptide GLP-1R agonists are in clinical development)[14,15], it is anticipated that the

low enough to ensure high confidence in participant safety, while some pharmacological effects are expected.

The dose range to be studied was selected to account for uncertainties in the projected C_{eff} and the projected therapeutic dose, while also bracketing the expected clinically efficacious dose range in humans for clinically relevant pharmacological activity and providing safety coverage for a wide range of PF-06954522 doses.

The projected exposures of PF-06954522 for each planned dose level, as well as the corresponding safety margins relative to human exposure limits are summarized in Table 3.

Table 3. Predicted Human Exposure and Safety Margins Following Administration of Single Oral Doses of PF-06954522

Dose (mg) ^a	Predic	ted Human PI	Predicted Safety Margin			
	Total Cmaxb	Total	C _{max} d	AUC ₂₄ d		
	(ng/mL)	AUC ₂₄ ^b	C_{max}^c	AUC ₂₄ ^c		
		$(ng \cdot h/mL)$	(ng/mL)	(ng•h/mL)		
CCI						

- a. Based on the available safety, tolerability and PK data, dose escalation may be adjusted to doses other than those outlined above with intermediate doses evaluated instead of or in addition to the planned dose levels with increments being approximately $\leq \frac{1}{2}$ -log (ie, approximately 3.3-fold) while always following dose escalation and stopping rules outlined in Section 6.6.1.
- Human PK profiles were predicted using a 1-compartment PK model with first-order absorption and elimination. The projected human PF-06954522 PK parameters outlined in Section 4.3.1 were used in the model.
- c. Unbound exposure values calculated after correcting for plasma protein binding in humans (CCI)
- d. Safety margins at the proposed doses were calculated based on the human exposure limits (total

 Which were based on the NOAEL exposures in the 8-week NHP GLP toxicity study after correcting for species difference in plasma protein binding.

Beyond the starting dose, the planned dose escalation procedure will be dictated by the rules summarized in Section 6.6.1. Assessment of the safety, tolerability, and PK after each single dose level will be conducted before escalating to the next dose level. The dose/exposure-escalation increments are planned to be up to approximate semi-logarithmic increases in exposure from the previous highest dose level that has been evaluated. If exposure exceeds the projected therapeutic range, or if changes in safety parameters are observed, smaller dose-escalation steps may be implemented. Dose-escalation is envisioned to proceed up to the highest dose deemed to be well tolerated with an acceptable safety profile, achievement of plasma exposures equivalent to the PK stopping limits (see Section 6.6.1).

The actual dose levels, target exposures, and/or dose level increments may be adjusted (higher or lower) during the study based on emerging human safety, tolerability, and PK data, but projected exposures will not exceed the predefined human exposure limits. Dose levels may also be repeated if warranted.

When the assessment of the effect of food on the PK of PF-06954522 is conducted, the dose level will be selected based on emerging safety, tolerability, and PK data from previous periods of this study. This will be assessed at a dose level that has been previously administered fasted within the same cohort (as outlined in Section 4.2).

